#### 4.10.1.3. WOMAC A (pain) Responder

Responders are defined as patients who have  $\geq 20\%$ ,  $\geq 30\%$ , or  $\geq 50\%$  decrease in the WOMAC A score from Baseline at a given visit (Weeks 1, 4, 8, 12, etc.). All study visits will be analyzed and presented.

Percentages will only be based on those with non-missing data. The number of patients who have missing data at each visit will be presented.

At each weekly assessment, proportions of FX006 responders will be compared to those responding in the placebo group using logistic regression, displaying the p-value and odds ratio (OR) (with CI) for each comparison. Study site and Baseline WOMAC A score will be included as covariates in the model.

Bar charts displaying the percentage of responders in each treatment group at each weekly assessment will be presented. Additionally, for Week 12, a continuous responder curve will display the cumulative proportion of responders on the y-axis versus percentage of improvement from Baseline on the x-axis, by treatment group.

---

#### 4.10.2. PGIC Score

##### 4.10.2.1. Continuous

The continuous PGIC score will be analyzed similar the WOMAC A (pain) analysis described in [Section 4.10.1.1](#). All available study visits will be analyzed and presented.

##### 4.10.2.2. Categorical

In addition, the PGIC scores will be collapsed and categorized as follows:

PGIC Score	Category
1 = Very Much Improved	A = Improved
2 = Much Improved	A = Improved
3 = Minimally Improved	B = Minimal – No Change
4 = No Change	B = Minimal – No Change
5 = Minimally Worse	B = Minimal – No Change
6 = Much Worse	C = Worse
7 = Very Much Worse	C = Worse

The percent of "Improved" subjects (among those patients with available data) at each study visit will be compared between the FX006 treatment group and the placebo group using logistic regression, displaying the p-value and OR (with CI) for each comparison. Baseline score of the endpoint, Baseline WOMAC score and study site will be covariates in each model. Bar charts by visit and treatment will be presented for the collapsed categories of "Improved", "Minimal – No Change", and "Worse".

---

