#### **4.2.3. Methods of Pooling Data**

Not applicable to the present study.

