#### **4.2.6. Subpopulations**

The analyses of WOMAC A, B and C change from Baseline and PGIC will be carried out for the subgroup of patients with WOMAC A (pain) average of Screening 2 and Day 1 scores of 5 to <6, 6 to <7, and ≥7 to 9, in order to assess any differences in treatment response in those groups, which were used as a stratification factor in randomization. These analyses will also be presented by unilateral/bilateral hip OA.

Other preplanned subgroups analyses (per aspiration status, Kellgren-Lawrence (K-L) grade, gender and the baseline pain score, etc.) will not be performed for Part I data. Other subgroups may be defined and explored after all pre-planned analyses have been completed to further elucidate study results.

---

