#### 4.10.3. OMERACT-OARSI and Responder Status

The OMERACT-OARSI responder criteria will also be used to define response (Pham, 2004) using a combination of pain, function, and a patient assessment to form a composite endpoint. The WOMAC A pain subscale, WOMAC C function subscale, and PGIC will be used to derive the composite responder variable. While the OMERACT-OARSI defines patient assessment in terms of numeric changes from Baseline, this study only collects the PGIC which is a static assessment collected at post-Baseline visits asking how the patient feels relative to Baseline; thus, the responder criteria is being modified slightly for this context to consider PGIC responders as those reporting "Very Much Improved" or "Much Improved" status. Patients will be considered responders at a given weekly assessment if they show:

- At least a 50% improvement from Baseline in the WOMAC A pain subscale and an absolute improvement of at least 20 points or at least a 50% improvement from Baseline in the WOMAC C function subscale and an absolute improvement of at least 20 points; OR
- At least two of the following:

- 
- At least a 20% improvement from Baseline in the WOMAC A pain subscale and an absolute improvement of at least 10 points
  - At least a 20% improvement from Baseline in the WOMAC C function subscale and an absolute improvement of at least 10 points
  - PGIC of "Very Much Improved" or "Much Improved"

It should be noted for the WOMAC Index that higher scores indicate worse function. Also, the absolute change in the responder criteria assumes the WOMAC is on a 100 point scale. To normalize the WOMAC A pain score, the sum of the 5 pain questions will be multiplied by 2. To normalize the WOMAC C function score, the sum of the 17 function questions will be multiplied by 0.59. Imputation of WOMAC A and C scores will follow the rules as displayed in [Section 4.2.8](#). If WOMAC A or C scores cannot be imputed due to the amount of missing data or patients are missing PGIC at a given week, those patients will be counted as missing/not evaluable in the tabulations.

The OMERACT analysis will be conducted in the same way as the WOMAC A (pain) Responder analysis as described in [Section 4.10.1.3](#). All available study visits will be analyzed and presented.

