Table 14.2.2.1.1.2	Analysis of Patient Global Impression of Change (PGIC), Patients with Baseline WOMAC A Pain Score 6 to $< 7$ (Full Analysis Set)
Table 14.2.2.1.1.3	Analysis of Patient Global Impression of Change (PGIC), Patients with Baseline WOMAC A Pain Score $\geq 7$ to 9 (Full Analysis Set)
Figure 14.2.2.1.1	LS Mean Change from Baseline (+/- SE) in Patient Global Impression of Change (PGIC) Over Time by Baseline WOMAC A Pain Score (Full Analysis Set)
Table 14.2.2.1.2.1	Analysis of Patient Global Impression of Change (PGIC), Patients with Unilateral Hip OA (Full Analysis Set)
Table 14.2.2.1.2.2	Analysis of Patient Global Impression of Change (PGIC), Patients with Bilateral Hip OA (Full Analysis Set)
Figure 14.2.2.1.2	LS Mean Change from Baseline (+/- SE) Patient Global Impression of Change (PGIC) by Unilateral/Bilateral Hip OA Over Time (Full Analysis Set)

---

---

Table 14.2.2.2	Analysis of Patient Global Impression of Change (PGIC) Results by Category (Full Analysis Set)
Figure 14.2.2.2	Patient Global Impression of Change (PGIC) Results by Category (Full Analysis Set)
Table 14.2.2.2.1.1	Analysis of Patient Global Impression of Change (PGIC) Results by Category, Patients with Baseline WOMAC A Pain Score 5 to <6 (Full Analysis Set)
Table 14.2.2.2.1.2	Analysis of Patient Global Impression of Change (PGIC) Results by Category, Patients with Baseline WOMAC A Pain Score 6 to <7 (Full Analysis Set)
Table 14.2.2.2.1.3	Analysis of Patient Global Impression of Change (PGIC) Results by Category, Patients with Baseline WOMAC A Pain Score $\geq 7$ to 9 (Full Analysis Set)
Figure 14.2.2.2.1	Patient Global Impression of Change (PGIC) Results by Category Baseline WOMAC A Pain Score (Full Analysis Set)
Table 14.2.2.2.2.1	Analysis of Patient Global Impression of Change (PGIC) Results by Category, Patients with Unilateral Hip OA (Full Analysis Set)
Table 14.2.2.2.2.2	Analysis of Patient Global Impression of Change (PGIC) Results by Category, Patients with Bilateral Hip OA (Full Analysis Set)
Figure 14.2.2.2.2	Patient Global Impression of Change (PGIC) Results by Category by Unilateral/Bilateral Hip OA (Full Analysis Set)
Table 14.2.3	Analysis of OMERACT-OARSI Responders (Full Analysis Set)
Figure 14.2.3.1.1	Proportion of OMERACT-OARSI Responders (Full Analysis Set)
Figure 14.2.3.1.2	Continuous OMERACT-OARSI Responder Curve at Week 12 (Full Analysis Set)
Table 14.2.4	Summary of Rescue Medication Usage (Full Analysis Set)

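### Study site in the pain-stratum PGIC 'Improved' logistic models (about 21 patients each), with no rule for separation, can leave the treatment odds ratio without a finite value

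*SAP*

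**What the plan says.** The covariates for the PGIC category model are set in SAP 4.10.2.2: "Baseline score of the endpoint, Baseline WOMAC score and study site will be covariates in each model". At each visit this logistic model is to give an odds ratio, confidence interval and p-value.

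SAP 4.2.6 carries PGIC into the three pain strata used at randomization: "The analyses of WOMAC A, B and C change from Baseline and PGIC will be carried out for the subgroup of patients". It adds: "These analyses will also be presented by unilateral/bilateral hip OA". SAP 7.1 confirms that the categorical model is meant as well as the continuous score, for example "Analysis of Patient Global Impression of Change (PGIC) Results by Category, Patients with Baseline WOMAC A Pain Score 5 to <6" and "Analysis of Patient Global Impression of Change (PGIC) Results by Category, Patients with Unilateral Hip OA".

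The other two responder outcomes also adjust for site, but are not listed by stratum. For WOMAC A response, SAP 4.10.1.3 says: "Study site and Baseline WOMAC A score will be included as covariates in the model". SAP 4.10.3 follows by cross-reference: "The OMERACT analysis will be conducted in the same way as the WOMAC A (pain) Responder analysis".

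No code is given for the logistic models. In the sample code for the MMRM (SAP 4.10.1.1) and the AUE analysis (4.10.1.2), site is a class variable. The only specific fallback in the SAP is for an unstructured MMRM covariance matrix that does not converge. SAP 4.2.1, 4.4 and 4.10.9 allow further sensitivity or post-hoc work in general terms.

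**The concern.** With one indicator per site, a site whose patients all had one arm, or all had one outcome, tells the model nothing about treatment. Spread 21 patients over 10 sites and there are about two per site, so much of the stratum drops out of the comparison. If the remaining sites all point the same way, once baseline WOMAC A is allowed for, the maximum-likelihood odds ratio is zero or infinite. The table would then show a meaningless estimate and interval. Because the Part I analysis is unblinded, any substitute method would be chosen with treatment known.

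The same sentence has a second, definite fault. It asks for a baseline value of the endpoint, but SAP Table 1 first schedules PGIC at Week 1, and SAP 4.10.3 describes PGIC as collected only after Baseline. That covariate cannot be fitted in any PGIC model.

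**Working it through.** **The plan's own figures.** The only computed sizes are for Part II (SAP 4.1), and they reproduce:
- Primary: 2 × (1.960 + 1.282)² × (2.0/0.65)² gives 199; 199/0.94 = 211.7, so 212 per arm.
- First key secondary: SD 2.125 and difference 0.68 give 206; 206/0.94 = 219.1, so 220 per arm.

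No figure is given for the Part I logistic models, so the rest is new.

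**Inputs from the documents.** About 70 patients randomized 1:1 (SAP 2.1, 4.1). Six had incomplete administration (4.2.7, Section 5). The FAS takes full doses only (3.1), so about 70 − 6 = 64. Three strata give 64/3 = about 21 if equal, and the smallest cannot exceed 21. Through Week 12 there are 3 strata × 4 visits = 12 stratum models, and 2 × 4 = 8 for unilateral/bilateral OA.

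**Assumed.** Number and evenness of sites, equal strata, response rates, and one model level per site.

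**Hand check without site.** Ignoring the baseline covariate, the odds ratio is not finite when an arm is all 'Improved' or has none. With 10 placebo and 11 FX006 patients, control rate 40% and true odds ratio 2.0 (FX006 rate 57.1%):

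0.4¹⁰ + 0.6¹⁰ + 0.571¹¹ + 0.429¹¹ = 0.0001 + 0.0060 + 0.0021 + 0.0001 = about 0.8%.

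At rates of 20% and 30%: 0.8¹⁰ + 0.7¹¹ − overlap = 0.107 + 0.020 − 0.002 = about 12.5%.

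**Hand check with site.** Take 10 sites of exactly two patients, with a 1/2 chance that a site has both arms. A site favours FX006 with probability ½ × 0.571 × 0.6 = 0.171, and placebo with ½ × 0.4 × 0.429 = 0.086. A finite odds ratio needs at least one site of each kind. So

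P(not finite) = (1 − 0.171)¹⁰ + (1 − 0.086)¹⁰ − (1 − 0.257)¹⁰ = 0.153 + 0.408 − 0.051 = about 51%.

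Adding baseline WOMAC A can only raise this. Real enrolment leaves some sites with more than two patients in a stratum, which lowers it, so simulation is needed.

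**Simulation, one stratum of 21 patients.** Each simulated data set was tested for whether the treatment coefficient is finite given site and baseline WOMAC A. Ranges cover even and uneven enrolment.

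| Method and setting | 5 sites | 8–12 sites | 20 sites | No site |
|---|---|---|---|---|
| Exact within-site check, control rate 40% | 8–13% | 21–36% (10) | 44–72% | about 1% |
| Same, control rate 30% | 12–17% | 24–44% (10) | 51–76% | 2.5–4% |
| Linear programs, blocks of 4, rates 30/50% or 20/30% | – | 17–44% (8); 24–56% (12) | 48–79% | 3–12% |
| Linear programs, true odds ratio 2.0 | 7–12% | 17–33% (10) | 46–62% | about 1% |

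A further repeat gave 11–13%, 18–37% (10 sites) and 40–71%. Taken together: about 7–17% at 5 sites, 17–44% at 10 and 44–79% at 20.

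**Stratum size.** At 10 sites: 45–70% with 16 patients, 5–17% with 28.

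**Any of the three strata at a given visit.** 30–47% at 5 sites, 57–78% at 10 and 83–98% at 20, against 5–12% without site.

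**Unilateral/bilateral.** With 32 patients per side: 2–8% at 10 sites and 8–30% at 20. With a side of 20: 23–47% and 48–77%.

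**Full set of 64.** No finite odds ratio in 0% at 8 sites, 0–0.5% at 12, 0.3–1.5% at 20–30 and 2–9% at 45. For a true odds ratio of 2.0 at 10 sites, the median fitted value is 2.3–2.4, with a standard error of the log odds ratio of 0.62–0.67. The shift is ln(2.3/2.0) = 0.14 to ln(2.4/2.0) = 0.18, about a quarter of a standard error.

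**Remedies in the stratum.** The SD of the log odds ratio is 0.9–1.0 without site, against 1.1–1.75 for Firth regression with site kept in.

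**The case against.** The case for leaving the plan alone is substantial. Every Part I endpoint is exploratory, with no multiplicity control. The listed key secondary is the PGIC score, and the categorical version is an addition to it. No stated decision rests on the stratum tables. A non-finite odds ratio is visible, and the SAP allows labelled post-hoc work. Protocol 9.2.4 names site as an efficacy covariate, and SAP Section 5 gives a reason for it. The frequency also depends on a site count that the documents do not give. All of this stands and limits the severity. It does not supply a rule for separation, and at 10 sites the planned stratum model still fails far more often than the same model without site.

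A reader might infer three stronger things.

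- *Site should come out of every responder model, and out of the stratum MMRMs.* The documents and figures do not support that. Full-set failures are rare and the shift is small. Part of it is ordinary small-sample bias: in one set of runs with a true odds ratio of 2.33, the model without site already gave 2.56. Those runs also put Wald type I error at 7–10% with site against 5.1% without, but Part I makes no confirmatory claim. In the stratum MMRM, the standard error with site is 0.93–1.07 times that without at 5 sites and 0.98–1.25 times at 10, which is a trade-off rather than a fault.
- *The SAP rules out pooling small sites.* SAP 4.2.3 says only "Not applicable to the present study" under a heading about pooling data, and does not mention sites.
- *Part I has 40–50 sites.* That figure in the Protocol synopsis is the plan for the whole study of about 510 patients, and enrolment was suspended before Part II.

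It may also be said that Firth regression with site would be enough. It gives a finite estimate, but in a 21-patient stratum a clearly less precise one.

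**Conclusion.** The point holds for the pain-stratum PGIC-category models, and for any unilateral/bilateral subgroup of similar size. As specified, one stratum's treatment odds ratio has no finite value in about 7–17% of data sets at 5 sites, 17–44% at 10 and 44–79% at 20. Without site it is about 1–4% in most settings and up to 12% at low response rates. These ranges rest on assumed site counts, enrolment patterns, response rates and equal strata, and on site being one level per site. Severity is minor. The missing PGIC baseline value is a plain error that needs no assumption.

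**What to change.** - In SAP 4.10.2.2 and 4.2.6, for the pain-stratum PGIC-category models and any unilateral/bilateral subgroup of similar size: omit study site and adjust for baseline WOMAC A only.
- Delete the baseline score of the endpoint from the 4.10.2.2 covariate sentence, and name the WOMAC subscale there as A.
- Fit these subgroup models by Firth-penalized logistic regression with a profile-likelihood confidence interval. Use the same method for any full-set responder model whose treatment odds ratio is not finite (4.10.1.3, 4.10.2.2, and 4.10.3 by cross-reference). Flag each use in the table.
- Declare this in SAP Section 5 as a departure from Protocol 9.2.4 for these subgroup models.
- Report the number of sites that enrolled Part I patients.
- Keep site in the full-set logistic models; conditional or Firth regression is optional there. Leave the MMRM, AUE and TSQM-9 models unchanged.

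The cost is a few sentences of SAP text. No new data are needed, and the site count can be stated without unblinding. There are two downsides. Between-site differences are not removed in the subgroup models: with strong site differences (logit SD 1.0, assumed), a true odds ratio of 2.0 is estimated at about 1.8. The subgroup odds ratios also stay imprecise: an SD of 0.9–1.0 on the log scale means that the upper 95% limit is about exp(2 × 1.96 × 0.9) = 34 to exp(2 × 1.96 × 1.0) = 50 times the lower. The change makes these estimates finite, not informative.

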#### 4.10.3. OMERACT-OARSI and Responder Status

The OMERACT-OARSI responder criteria will also be used to define response (Pham, 2004) using a combination of pain, function, and a patient assessment to form a composite endpoint. The WOMAC A pain subscale, WOMAC C function subscale, and PGIC will be used to derive the composite responder variable. While the OMERACT-OARSI defines patient assessment in terms of numeric changes from Baseline, this study only collects the PGIC which is a static assessment collected at post-Baseline visits asking how the patient feels relative to Baseline; thus, the responder criteria is being modified slightly for this context to consider PGIC responders as those reporting "Very Much Improved" or "Much Improved" status. Patients will be considered responders at a given weekly assessment if they show:

- At least a 50% improvement from Baseline in the WOMAC A pain subscale and an absolute improvement of at least 20 points or at least a 50% improvement from Baseline in the WOMAC C function subscale and an absolute improvement of at least 20 points; OR
- At least two of the following:

- 
- At least a 20% improvement from Baseline in the WOMAC A pain subscale and an absolute improvement of at least 10 points
  - At least a 20% improvement from Baseline in the WOMAC C function subscale and an absolute improvement of at least 10 points
  - PGIC of "Very Much Improved" or "Much Improved"

It should be noted for the WOMAC Index that higher scores indicate worse function. Also, the absolute change in the responder criteria assumes the WOMAC is on a 100 point scale. To normalize the WOMAC A pain score, the sum of the 5 pain questions will be multiplied by 2. To normalize the WOMAC C function score, the sum of the 17 function questions will be multiplied by 0.59. Imputation of WOMAC A and C scores will follow the rules as displayed in [Section 4.2.8](#). If WOMAC A or C scores cannot be imputed due to the amount of missing data or patients are missing PGIC at a given week, those patients will be counted as missing/not evaluable in the tabulations.

The OMERACT analysis will be conducted in the same way as the WOMAC A (pain) Responder analysis as described in [Section 4.10.1.3](#). All available study visits will be analyzed and presented.

#### **4.10.4. Consumption of Rescue Medications**

A descriptive summary of the average rescue medications taken per patient each day will be presented by visit and overall.

Use of rescue medication is recorded on the Rescue Medication Accountability CRF. Each tablet of rescue medication contains 500mg of acetaminophen (paracetamol). The mean number of rescue medication tablets used per day will be computed for each patient according to the following algorithm:

1. At each visit, the number of pills taken will be determined by subtracting the number returned at the current visit by the number dispensed at the previous visit.
2. The number of days between the current and previous visits will be calculated by using the dates of each visit.
3. The average number of pills taken per day will be calculated by dividing the total number of pills used between visits by the total days between visits.

The value for each visit indicates the daily average for the period from the previous visit to the current visit. For example, the value for the Week 8 visit represents the daily average over the time period from Week 4 to Week 8.

---

Patients who do not report use of rescue medications at a given visit will be counted as having used 0 tablets when calculating the mean number of tablets used, and patients will only be analyzed through the time of study discontinuation or study completion.

Rescue medication consumption will be analyzed similar the WOMAC A (pain) analysis described in [Section 4.10.1.1](#). All available study visits will be analyzed and presented.

Rescue medication usage and accountability data will be provided in by-patient listings.

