#### **4.2.8. Missing, Unused, and Spurious Data**

Missing values will not be imputed and data will be analyzed “as observed”.

For WOMAC, the rules as described in the WOMAC user guide (Bellamy 2011) will be used. Specifically, if at least 2 pain, both stiffness, or at least 4 function items are missing, the patient's response will be regarded as invalid and the score for that given subscale as well as the total score will be left missing. If no more than 1 pain, 1 stiffness, and less than 4 function items are missing, the missing value in a given subscale will be imputed using the average of all items in the given subscale. Imputed WOMAC scores will be flagged in the data listings.

For the HOOS-QOL subscale, the rules as described in HOOS Scoring 2013 (<http://www.koos.nu/>) will be used. Specifically, the score is only calculated if 50% items (2 out of 4) are non-missing. Otherwise the score will be set to missing.

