#### 4.10.1.1. Change from Baseline

For the WOMAC subscales, scores at each assessment time point (Baseline, Week 1, Week 4, Week 8, Week 12, etc.) will be calculated as the average of the responses to all questions in the subscale. Total score will be computed as the average of the average responses on each of the subscales (e.g. Average A + Average B + Average C divided by 3). This will provide a uniform scoring of 0 to 10 for each subscale and easier interpretation. Imputation rules are as presented in [Section 4.2.8](#).

Each of the WOMAC subscales will be analyzed separately using a longitudinal MMRM with fixed effects for Baseline score for the endpoint, treatment group, study week, treatment-by-week interaction, study site, and Baseline WOMAC A score. The analysis will include all study weeks of data, and not be confined to only that at Baseline and Week 12. Subject will be the random effect. Treatment differences from placebo will be estimated via least squares (LS) means from the analysis model along with 95% CIs, and associated 2-sided p-values. This model assumes missing at random and includes only observed data.

This model will be run using the SAS/STAT PROC MIXED procedure with an unstructured correlation matrix to model the within-subject errors. If the unstructured covariance matrix does not converge when fitting the mixed model, further investigation into the most appropriate correlation matrix will be conducted. The final selection of the correlation matrix to be used in fitting the mixed model will be presented in the table output and fully documented in the results section of the CSR.

Sample SAS code that can be used to implement the mixed analysis is provided below:

```
proc mixed data= dsin1 method=reml;
  class subjid armcd avisitn site;
  model chg = base armcd avisitn armcd*avisitn site base_womaca;
  repeated avisitn /type=un subject=subjid;
  lsmeans armcd/diff=control ('0') cl;
  /*[where 0 represents treatment=placebo]*/
  lsmeans armcd*avisitn /pdiff cl;
run;
```

Descriptive statistics will also be presented and will include number of observations, unadjusted mean, SD, median, minimum and maximum. Change from Baseline will also be presented. For the change from Baseline calculation, Baseline is the WOMAC result obtained on Day 1 prior to first dose. The adjusted change from Baseline will also be presented using results from the MMRM.

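### The rule scoring unreported rescue use as 0 tablets does not separate confirmed no use from an absent count, so it can impute the best value where SAP 4.2.8 allows no imputation

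*SAP*

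**What the plan says.** SAP 4.10.4 names the data source: "Use of rescue medication is recorded on the Rescue Medication Accountability CRF". Step 1 obtains tablets taken by "subtracting the number returned at the current visit by the number dispensed at the previous visit", which must be meant as dispensed minus returned. Step 2 takes the days between the two visit dates. Step 3 obtains the daily average by "dividing the total number of pills used between visits by the total days between visits".

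The scoring rule follows: "Patients who do not report use of rescue medications at a given visit will be counted as having used 0 tablets". The same sentence limits it, in that "patients will only be analyzed through the time of study discontinuation or study completion". The endpoint then goes to a model: "Rescue medication consumption will be analyzed similar the WOMAC A (pain) analysis" of SAP 4.10.1.1, about which that section says "This model assumes missing at random and includes only observed data".

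The general rule in SAP 4.2.8 is that "Missing values will not be imputed and data will be analyzed" as observed. The exceptions given there cover missing items within WOMAC and HOOS-QOL only. SAP section 5 (changes to planned analyses) does not mention the zero rule.

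**The concern.** The endpoint is a count, so a true zero already comes out of step 1 when every dispensed tablet is returned. The schedules of assessments list dispensing and accountability but no diary or other patient report of rescue use. It is therefore unclear what reporting the zero rule refers to. One event it can describe is a visit without a usable count: the visit was missed, the count was not done, or the bottle was not brought back and the field was left blank.

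If the rule covers those cases, an unknown value is replaced by the most favourable one and enters the mixed model as if observed. Protocol 7.3.3 presents rescue use as further confirmation of symptomatic improvement, so a distortion here affects how the pain result is read. Protocol 9.1 also expects Parts I and II to be analysed in the same way, so the rule could carry over to the Part II plan.

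**Working it through.** **Nothing to reproduce.** The documents give no expected rescue use, no rate of absent counts and no power statement for this endpoint. Mean use and absence rates below are assumptions.

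**Does the rule reach absent counts?** The text does not say. The cut-off at discontinuation or completion points that way: a rule confined to recorded no use would never reach visits after a patient has left, so it would not need the limit. This is an inference from the wording.

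**Effect on an arm mean.** Let mu be true tablets/day and m the share of on-study counts that are absent and scored 0. If patients with absent counts use as much as the others, the expected mean is (1 - m) x mu. With mu = 2:

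| m | Mean under the zero rule | Mean if left missing |
|---|---|---|
| 2% | 1.96 | 2.00 |
| 5% | 1.90 | 2.00 |
| 10% | 1.80 | 2.00 |
| 20% | 1.60 | 2.00 |

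**Effect on the difference.** Assume true means of 2.0 (placebo) and 1.5 (FX006), a difference of -0.50.

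| Absent, placebo / FX006 | Placebo | FX006 | Difference | Change in size |
|---|---|---|---|---|
| 10% / 10% | 0.90 x 2.0 = 1.80 | 0.90 x 1.5 = 1.35 | -0.45 | 10% smaller |
| 15% / 5% | 0.85 x 2.0 = 1.70 | 0.95 x 1.5 = 1.425 | -0.275 | 45% smaller |
| 5% / 15% | 0.95 x 2.0 = 1.90 | 0.85 x 1.5 = 1.275 | -0.625 | 25% larger |

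**No true difference.** The spurious benefit for FX006 is mu x (m on FX006 - m on placebo). With 5% absent on placebo and 10% to 20% on FX006, it runs from 1 x 0.05 = 0.05 to 3 x 0.15 = 0.45 tablets/day for mu of 1 to 3. It is zero when the shares are equal and reverses sign when placebo has more absent counts.

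**Unreturned bottle.** The SAP gives no rule, and two applications of its text disagree. Suppose a 28-day supply at the protocol's cap of 6 tablets per day, that is 6 x 28 = 168 tablets (the quantity dispensed is an assumption). If the form records 0 returned, step 1 gives 168 and step 3 gives 168 / 28 = 6.0 tablets/day. If the field is blank and the zero rule applies, the value is 0. In an arm of about 35, that one patient moves the mean by 6 / 35 = 0.17.

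**Missed Week 8.** At a true 2 tablets/day, 2 x 56 = 112 tablets are used from Week 4 to Week 12. Week 8 may be scored 0. Week 12 is 112 / 56 = 2.0 if divided by days since the last attended visit, but 112 / 28 = 4.0 if divided by the nominal interval.

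**The case against.** The strongest reply is that the sentence never mentions absent counts. A patient who attends and says that none was taken has not reported use, and scoring that as 0 is an observation and not an imputation. Separate listings are planned for usage and for accountability, so the form may hold a usage item that cannot be seen in the documents. This stands: the conflict with SAP 4.2.8 is conditional on the rule covering absent counts.

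Several narrower points also stand:

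- Some zeros the rule adds may be right. Footnote e to the double-blind schedule and Protocol 7.9.12 have bottles supplied as needed, whereas Protocol 7.6.3 has a new supply issued at every visit. A patient who needed no new bottle may have no dispensed figure for step 1.
- Patients who leave the study are not zero-filled afterwards.
- Step 2 works from visit dates, so averaging over a longer interval after a missed visit is its natural result, though the SAP does not say so.
- The plan assumes only 6% early discontinuation overall. Nothing in it supports 15% absent counts among patients still on study, or a split between arms.
- By-patient listings would let a reader find the zeros, and optional missing-data sensitivity analyses are allowed for in SAP 4.10.9.

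A reader might infer that the SAP turns every unreturned bottle and missed visit into perfect pain control, in flat contradiction of its own missing-data rule. The documents do not support that. Neither event is named, a bottle entered as 0 returned counts as full use, and rescue tablets do not enter the WOMAC, PGIC or responder derivations.

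The replies do not remove the ambiguity. Two programmers following this section could give the same patient opposite extreme values.

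**Conclusion.** The point holds as a defect in a stated scoring rule. SAP 4.10.4 does not distinguish confirmed no use from an absent count. Where it is applied to absent on-study counts, it is best-value single imputation, at odds with SAP 4.2.8 and with a model said to use observed data only.

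Each arm mean then shrinks by its share of absent counts, 2% to 20% over the assumed range. Equal shares shrink a true difference and create no false benefit; unequal shares can bias it either way. Neither direction nor size can be determined from the documents. The formulas also assume that absence of a count is unrelated to how much was taken.

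Severity is minor to moderate. Rescue use is an additional secondary endpoint, and all Part I endpoints are exploratory, with about 35 patients per arm and no multiplicity control. The rule should nevertheless be settled before it is carried into Part II.

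**What to change.** Replace the zero-rule sentence in SAP 4.10.4 with the following:

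1. Score 0 only when the accountability record confirms no use: all dispensed tablets returned, or an explicit entry that none was taken, including where no new bottle was issued.
2. Otherwise leave the interval missing and let the mixed model handle it, as SAP 4.2.8 already implies.
3. Treat an unreturned bottle as a missing count, neither 0 nor full use.
4. After a missed visit, use the tablets and actual days since the last available count.
5. Report the number of missing counts by arm and visit.

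A sensitivity analysis scoring missing counts first as 0 and then as all dispensed tablets used would show whether the choice matters. The passages on when a new bottle is issued should be reconciled, because step 1 depends on them.

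The cost is a few lines of SAP text, one added tabulation and slightly fewer non-missing values. Leaving counts missing removes the shrinkage only if absence is unrelated to use, or is explained by the data in the model.
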